Clinical Study Type	Post-Market Pivotal /IDE Study
Product Name	BIS™ Complete Monitoring System
Sponsor	Medtronic, Patient Monitoring & Respiratory Interventions [name]
Indication under investigation	Intended for use in pediatric patients (4 years old and above)
Investigation Purpose	The purpose of this study is to investigate the relationship between BIS™ values including EEG profile and anesthetic agents in the pediatric population
Product Status	BIS™ is commercially available in the United States
Primary Objective(s) and/or Endpoint(s)	Primary objective: To characterize BIS™ performance with the anesthetic agent in pediatric patients ages 4 to 18 years Primary endpoint: The end-tidal sevoflurane concentration in both patient groups acquired during maintenance of anesthesia. The study will be considered a success if the primary objective, achieving statistical and clinical significance in obtaining the end-tidal sevoflurane concentration during maintenance in both patient groups, is achieved.
Secondary Objective(s) and/or Endpoint(s)	Secondary endpoint(s): 
Recovery assessments in patients receiving monitoring compared to standard anesthetic practice (instructions for collection contained in Study Procedures and Assessments):

Medtronic Business Restricted

	
• Emergence• Emergence is defined as the time when any of the following first occurred:
• Eyes open spontaneously• Crying or phonating• Purposeful movements• PACU discharge readiness using Modified Aldrete Score [15,16]• Anesthesia Airway Management (AAM) will be noted:
○ Awake and Deep Extubation (endotracheal tube (EET) vs. laryngeal mask airway (LMA)○ Airway reflexes (e.g., coughing, choking, laryngospasm) 
Additional/Exploratory Endpoints:
 
• Clinical Anesthesia Assessment, recorded as the incidence of movements, grimacing, eye opening, tearing, sweating, mydriasis and cardiovascular changes while undergoing anesthesia• Pediatric Anesthesia Emergence Delirium (PAED)• Wong-Baker FACES Pain Rating Score

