Randomization	Subjects will be randomized 1:1 within each age group and each site to one of the two groups, standard practice (SP) or BIS™ (BIS) groups.
Sample Size	The first 2 - 4 subjects at each site will be enrolled to train the site team on the new technology and to determine the quality of data collection prior to randomization (n = 16-32). They will not be randomized and will not be included in the final analysis. For the analysis, a minimum of 36 subjects are required in each age group (18 per treatment group) for a minimum of 108 qualifying data sets. Subjects with non-qualifying data sets will be rejected and replaced with a newly randomized subject. This sample size was independently powered for each of the 3 age groups based on data from a previously published study conducted by Emory University.
Planned number of sites	Eight investigational sites in the US
Inclusion/Exclusion Criteria	
Inclusion Criteria:
 
1) Pediatric Subjects (ASA PS I or II or III) aged: 4 years to 18 years scheduled for procedures with sedation where the process of assessment will not interfere with the procedure, progress, or patient care 
Exclusion Criteria:
 
1) Has severe contact allergies that may cause a reaction to standard adhesive materials found in pulse oximetry sensors, ECG electrodes, respiration monitor electrodes, or other medical sensors2) Known neurological disorder (e.g., epilepsy, the presence of a brain tumor, a history of brain surgery, hydrocephalic disorders, depression needing treatment with anti-depressive drugs, a history of brain trauma, hemiplegia, demyelinating disorders, cerebral palsy, congenital anomalies of the brain or spinal cord, or other known neurologic disorders)3) Severe developmental delay per assessment of investigator or report of parent/guardian4) Airway abnormalities5) Pregnancy; subjects of childbearing potential will have a urine screen for pregnancy before surgery6) If the process of assessment will interfere with the procedure or the progress of the procedure7) Taking psychoactive medications

Medtronic Business Restricted

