In the patients 0–6 months of age undergoing IH, sevoflurane concentrations during maintenance (2.0 ± 0.4% SP, 0.9 ± 0.8 BIS™), during the last 15 minutes (1.6 ± 0.4% SP, 0.6 ± 0.6% BIS™), and at the end of the procedure (1.1 ± 0.6% SP, 0.3 ± 0.3% BIS™) were smaller in the BIS™ group, **Table**. Emergence and recovery measures, **Table**, were unaffected by BIS™ titration. In the children 6 months to 3 years of age, there were no significant differences between the SP and BIS™ groups in anesthetic use or recovery measures.

Table 2: Intraoperative Data for Control, Standard Practice (SP), and BIS Groups (mean \pm SD)

	Control	SP	BIS
Infants (age 0–6 mo), hernia repair			
Average ET sevoflurane, maintenance (%)	2.2 \pm 0.7	2.0 \pm 0.4	0.9 \pm 0.8*
Average ET sevoflurane, last 15 min (%)	2.0 \pm 0.9	1.6 \pm 0.4	0.6 \pm 0.6*
Average ET sevoflurane, end of procedure (%)	1.5 \pm 0.9	1.1 \pm 0.6	0.3 \pm 0.3*
BIS™ maintenance	34.9 \pm 5.8	36.2 \pm 11.8	35.7 \pm 9.6
BIS™ last 15 min	34.9 \pm 7.0	40.4 \pm 12.5	41.0 \pm 10.5
BIS™ end of procedure	37.7 \pm 7.1	43.1 \pm 17.5	48.3 \pm 12.9
Infants and small children (6 mo–3 yr), hernia repair			
Average ET sevoflurane, maintenance (%)	1.8 \pm 0.4	2.3 \pm 0.6	2.2 \pm 0.5
Average ET sevoflurane, last 15 min (%)	2.0 \pm 0.7	2.0 \pm 0.6	1.9 \pm 0.5
Average ET sevoflurane, end of procedure (%)	1.5 \pm 0.9	1.4 \pm 0.8	1.2 \pm 0.6
BIS™ maintenance	55.8 \pm 15.2	50.0 \pm 14.1	54.8 \pm 9.1
BIS™ last 15 min	51.8 \pm 14.4	54.5 \pm 14.7	55.9 \pm 10.4
BIS™ end of procedure	56.2 \pm 18.4	61.4 \pm 15.3	64.5 \pm 10.1
Children (age 3–18 yr), tonsillectomy and/or adenoidectomy			
Average ET sevoflurane, maintenance (%)	2.4 \pm 0.4	2.4 \pm 0.6	1.8 \pm 0.4*
Average ET sevoflurane, last 15 min (%)	2.2 \pm 0.5	2.1 \pm 0.7	1.6 \pm 0.6*
Average ET sevoflurane, end of procedure (%)	1.6 \pm 0.7	1.5 \pm 0.7	1.1 \pm 0.6
BIS™ maintenance	37.2 \pm 7.5	39.6 \pm 11.5	47.2 \pm 10.1
BIS™ last 15 min	43.6 \pm 11.2	44.8 \pm 11.3	55.7 \pm 7.9*
BIS™ end of procedure	50.1 \pm 15.3	53.0 \pm 16.0	63.0 \pm 8.6*

ET = end-Tidal; SP = Standard Practice group; BIS = Bispectral Index group

* P < 0.05 versus SP group.

Table 3: Time from End of Procedure Needed to Achieve the Primary Recovery End Points for the Control, SP, and BIS groups (mean \pm D)

	Control	SP	BIS
Infants (age 0–6 mo), hernia repair			
First response (min)	3.3 \pm 1.8	4.3 \pm 4.0	2.9 \pm 2.6
Extubation (min)	10.9 \pm 7.5	9.3 \pm 8.9	5.0 \pm 2.6

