10.8 Randomization and Treatment Assignment

Prior to Randomization, 2 - 4 subjects from each site will be consented and enrolled. The data will be used to train on the new technology use, and to review the quality of the data collection, refer to *Section 10.2*.

Subjects are eligible for randomization assignment after study enrollment and verification of eligibility criteria. Subjects will be randomized in a 1:1 fashion to the BIS™ group or standard practice group using the RDC electronic system. Randomization schedules will be created by a Medtronic statistician, and randomization assignments will be automatically populated on the Randomization e-CRF after subject consent and eligibility verification have been entered in RDC. The randomization schedule will be stratified by age group and the study site to ensure 1:1 randomization within each study site.

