14.1 General Aspects of Analysis

Standard demographic information and baseline characteristics will be summarized using descriptive statistics. For safety assessments, adverse events (AEs) will be summarized using frequency counts and percentages. Descriptive statistics will be provided by severity and relationship as needed.

The primary endpoint will be collected as a continuous variable every minute along with the BIS values. The primary analysis will be based on all evaluable data (excluding training subjects). Normality of data will be tested using the Kolmogorov-Smirnov test. Depending on whether normality assumption holds, a two-group t-test or Wilcoxon rank-sum test will be used to compare between the two treatment groups. A *P*-value of less than 0.05 is considered statistically significant unless otherwise specified.

The training subjects will not be included in the analysis set for the primary and secondary endpoints. The training subjects will be summarized descriptively and separately. Any specific findings from these subjects will be noted and discussed in the study report.

The following secondary endpoints will be evaluated:

- Time to first response (emergence)
- Time to PACU discharge readiness using Modified Aldrete Score
- Time to extubation

Upon meeting the primary endpoint, the secondary endpoints will be evaluated using the Holm-Bonferroni method. The method is a sequentially rejective multiple test procedure used to adjust multiplicity and to ensure the overall type I error rate is controlled at the 0.05 level. For statistical inferences, categorical variables will be evaluated using the Chi-square test or Fisher's exact test, and continuous variables will be evaluated using the t-test or Wilcoxon rank-sum test as appropriate. The analysis details will be clearly specified in the Statistical Analysis Plan.

Data Poolability

The clinical study will be conducted under a common protocol for each investigational site with the intention of pooling the data for analysis. Every effort will be made to promote consistency in study execution at each study site.

An assessment of data poolability of the sites will be performed using a mixed-effect model for the primary endpoint. A significance level of 0.15 will be considered. Sites with fewer than five subjects will be combined into large sites to ensure statistical robustness.

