If the sites are found to be significantly heterogeneous with respect to the primary endpoint, additional analyses will be conducted to further assess differences between sites in baseline and procedural variables that might contribute the differences.

Medtronic Business Restricted

Missing Data

The primary analysis will include all evaluable data and missing values will not be imputed. BIS™ values that are outside of the specified range of 45 – 60 during maintenance of anesthesia for >35% of the maintenance duration will be considered a protocol deviation and will result in an exclusion of the subject from the primary analysis. The excluded subject will be replaced, and data from all excluded subjects will be noted and discussed in the final study report. Additionally, sensitivity analysis (e.g., multiple imputation) may be performed as appropriate to assess the robustness of study results.

Additional Summaries and Considerations

Cardiovascular variables will be summarized for both treatment groups. The incidence of hypotension will be summarized and compared to anesthesia sedation levels.

The anesthetic requirements with the BIS™ value, the percentage of time during maintenance with BIS™ value within the specified ranges, and number of episodes and duration of burst suppression will be assessed for the BIS and SP groups.

Additional endpoints, including the PAED scale, PACU discharge readiness and a subgroup analysis for subjects requiring neuromuscular blockade, will be evaluated by using descriptive statistics and compared between both groups.

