14.2 Sample Size Determination

The first 2 - 4 subjects at each site will be enrolled to train the site team on the new technology and to determine the quality of data collection prior to randomization (n = 16-32). They will not be randomized and will not be included in the final analysis. For the analysis, a minimum of 36 subjects are required in each age group (18 per treatment group) for a minimum of 108 qualifying data sets. Subjects with non-qualifying data sets will be rejected and replaced with a newly randomized subject. This sample size was independently powered for each of the 3 age groups based on data from a previously published study conducted by Emory University.[13] The sample size will provide more than 80% power to detect a difference of 0.5% in end-tidal sevoflurane concentration between the BIS™ and SP groups with a common standard deviation of 0.5% and two-sided significance level of 0.05.

15. Ethics

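### The primary test ignores the age-group and site strata used to randomise, so it loses some precision if they affect end-tidal sevoflurane; an adjusted pooled difference should be primary and should define success

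*Protocol*

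**What the plan says.** The Synopsis (Randomization) states: "Subjects will be randomized 1:1 within each age group and each site to one of the two groups". Protocol 10.8 repeats it: "The randomization schedule will be stratified by age group and the study site to ensure 1:1 randomization within each study site".

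The primary comparison is in Protocol 14.1: "Depending on whether normality assumption holds, a two-group t-test or Wilcoxon rank-sum test will be used to compare between the two treatment groups". SAP 7.9 carries the same rule. Neither has a term for age group or site.

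Site appears in the poolability assessment (Protocol 14.1, SAP 7.3), a mixed-effect model judged at 0.15. If sites differ, "additional analyses will be conducted to further assess differences between sites in baseline and procedural variables"; the primary test stays as it was.

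Protocol 14.2 says "This sample size was independently powered for each of the 3 age groups", with 18 per arm in each. The success statement in the Synopsis and Protocol 5.2.1 asks for "achieving statistical and clinical significance in obtaining the end-tidal sevoflurane concentration during maintenance in both patient groups" and does not mention age groups. SAP 7.5 plans no multiplicity adjustment. SAP 7.9 applies Holm-Bonferroni, but only to secondary endpoints once the primary has been met.

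**The concern.** Stratified allocation balances site and age group between arms. A test that ignores those factors still counts their variation as noise, so its standard error is larger than the true sampling variation of the difference. The benefit bought by stratifying is partly thrown away at the analysis.

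A linked question is which comparison decides success. The sample size is justified one age group at a time, while the test sentence describes a single comparison of two arms. A precise primary analysis has to settle both what it adjusts for and which difference it judges.

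**Working it through.** **Inputs from the documents.** 18 per arm in each of 3 age groups (54 per arm pooled), difference 0.5%, common SD 0.5%, two-sided alpha 0.05 (Protocol 14.2); eight sites (Synopsis). Three age groups by eight sites is 24 strata, averaging 108/24 = 4.5 subjects each.

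**Assumed, because the documents do not say.** Share of variance due to site: 10%, 20% or 40%. Permuted blocks of 4. Site shares of accrual 30/20/15/10/10/5/5/5%.

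**1. The stated power.** Noncentrality = 0.5 / (0.5 × √(2/18)) = 3.0 on 34 df, giving 83.0% by t-test (85.1% by normal approximation). The claim of more than 80% reproduces. At 54 per arm the noncentrality is 0.5 / (0.5 × √(2/54)) = 5.20 and power is 99.9%.

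**2. The limit under perfect balance.** If the strata explain a share R² of variance and are exactly balanced, the true variance of the difference is (1 − R²) times what the t-test uses. Type I error is then 2 × [1 − Φ(1.96/√(1 − R²))], and the implied interval is 1/√(1 − R²) times too wide.

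| R² | Type I error | Width ratio |
|---|---|---|
| 0 | 5.0% | 1.00 |
| 10% | 3.9% | 1.05 |
| 20% | 2.8% | 1.12 |
| 40% | 1.1% | 1.29 |

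**3. A realistic case.** With about one block of 4 per stratum, balance is only partial. Separate simulations of the assumed set-up, with no exclusions and pooled N = 108, gave:

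| Site share | Planned type I error | Implied width, planned / adjusted |
|---|---|---|
| 0 | 4.9–5.0% | 0.99 |
| 10% | 4.2–4.4% | 1.03 |
| 20% | 3.6–3.7% | 1.08 |
| 40% | 2.4–2.6% | 1.21–1.22 |

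The adjusted model held 4.9–5.1% in the largest run (30,000 trials per scenario). These runs stop at 36 qualifying subjects per age group. Continuing until both arms reach 18, as Protocol 14.2 requires, gives nearly the same planned size: 4.2–4.4%, 3.6–3.7% and 2.5%.

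**4. When age group matters too.** A separate simulation used equal expected accrual by site and split R² evenly between age and site. Planned t-test size was 4.1%, 3.1% and 1.8% at total R² of 10%, 20% and 40%; the Wilcoxon test was similar (4.1%, 3.1%, 1.7%). At R² = 20% and a true difference of 0.25%, power was 65% unadjusted and 73% adjusted. At 0.5% it exceeded 99% either way.

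**5. Age-group comparisons.** When accrual runs until both arms reach 18, adjusting for site adds roughly 2–3, 4–5 and 6–7 points of per-age power at site shares of 10%, 20% and 40%. These gains come from a common-variance model and are only indicative.

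**6. The possible success rules.**
- All three age groups must succeed: 0.830³ = 57% power.
- Any one suffices at unadjusted 0.05: 1 − 0.95³ = 14.3% family-wise error.
- One pooled difference: 5% error, 99.9% power at the design difference.

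**The case against.** The strongest reply is that the planned test is valid as it stands. With one value per subject and no stratum effect it is correctly sized; with a stratum effect it errs on the safe side. Pooled power is above 99% and the stated per-age power reproduces. The whole loss rests on an assumed site share and block size; stratifying without blocking would leave the size at about 5%. All of this stands, and it is why the point concerns efficiency and not validity.

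It is also true that no confidence interval for the primary difference is planned. The only one in SAP 7.9 is for the EC50, so the width ratios describe the interval implied by the planned test.

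A reader might infer that omitting the strata inflates false positives. The direction is the opposite. A reader might also infer that the plan carries a 14% family-wise error because three age groups were powered and SAP 7.5 makes no adjustment. The documents do not support that: nowhere is success allowed on any one age group, and Protocol 14.1 and SAP 7.9 read most naturally as one pooled comparison. The 14% and 57% figures show why the rule should be stated; they are not properties of the plan as written.

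What remains is that strata worth randomising on are worth using in the analysis, and that doing so costs almost nothing.

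**Conclusion.** The point holds as an avoidable loss of precision. Under the assumptions above, the planned pooled test runs at about 4%, 3.7% or 2.5% instead of 5% for site shares of 10%, 20% or 40%, with an implied interval about 3%, 8% or 21% wider than necessary. If neither site nor age group affects end-tidal sevoflurane, nothing is lost. At the design difference the pooled conclusion would rarely change; the benefit is a tighter estimate and better age-group estimates.

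Adjustment should not be read as protection against the exclusion rule. Protocol 14.2 says "Subjects with non-qualifying data sets will be rejected and replaced with a newly randomized subject", and Protocol 10.9.3.3 applies a BIS-range exclusion to the BIS arm. Any bias from removing and replacing those subjects is a separate matter that a stratum term does not address.

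**What to change.** 1. In Protocol 14.1 and SAP 7.9, make the primary analysis a linear model of each subject's mean maintenance end-tidal sevoflurane on arm, age group and site, merging small sites under the existing rule. The per-subject mean matches the quantity in Protocol 4.1.3.2, Table 2 ("Average ET sevoflurane, maintenance").
2. Use standard errors that let the residual variance differ by arm. That table gives SDs of 0.6 (SP) and 0.4 (BIS) at ages 3–18. Report the adjusted difference with a 95% CI.
3. Judge success on that single pooled adjusted difference at 0.05, and say so in the Synopsis and Protocol 5.2.1.
4. Report the three age-group differences from the same model with arm-by-age terms, as estimates with CIs and not as success tests. SAP 7.5 then needs no change for the primary endpoint.
5. Keep the planned t-test or Wilcoxon test as a sensitivity analysis.
6. In Protocol 14.2, note that the power of more than 80% (83%) applies to each age-group comparison separately.

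The cost is wording; arm, age group and site are already recorded. If site has no effect, about one point of power is lost: in simulation, 79.8% to 78.9% for the pooled comparison at a difference of 0.272%. The extra cost of arm-specific variances was not computed separately.

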	
8) Taking any medications that may have an impact on the Central Nervous System (CNS)
 
9) Planned use of any regional anesthesia; a local field block is not included in this exclusion and can be used at the discretion of the anesthesia provider
 
10) Planned use of dexmedetomidine (Precedex)
 
11) Refusal to participate in the study

Study Procedures and Assessments	
BIS™ Group:
 
Baseline/Enrollment Visit:
 
• Informed Consent• Review of Inclusion/Exclusion• Demographics• Medical History• Pre-operative vitals obtained in pre-operative holding 
Procedure:
 
• Randomization: Prior to Procedure• Induction and Maintenance:• BIS™ sensor positioning and validation of appropriate impedance of electrodes• Clinical Anesthesia Assessment including incidence of:
• Movement• Grimacing• Eye opening• Tearing• Sweating• Mydriasis• Cardiovascular changes• End of Procedure:
• Collection of BIS™ sensor placement, monitoring of cardiovascular variables, event markers and assessments• Recovery:

- Anesthesia Airway management
- Collection of incidents of post- op nausea
- Pediatric Anesthesia Emergence Delirium (PAED)
- Wong-Baker FACES Pain Rating Score when subject is awake
- Time of PACU Discharge

SP Group:

Baseline/Enrollment Visit:

- Informed Consent
- Review of Inclusion/Exclusion
- Demographics
- Medical History
- Pre-operative vitals obtained in pre-operative holding

Procedure:

- Randomization: Prior to Procedure
- Induction and Maintenance:
- BIS™ sensor positioning and validation of appropriate impedance of electrodes
- Clinical Anesthesia Assessment including incidence of:
 - Movement
 - Grimacing
 - Eye opening
 - Tearing
 - Sweating
 - Mydriasis
- Cardiovascular changes
- BIS™ monitor concealing: done to ensure that the clinician is blinded to the BIS™ values and that the BIS™ value is not used to guide the conduct of the anesthetic. The signal quality index (SQI) number will be visible to the anesthesiologist during the case to capture a good quality signal. The details on SQI monitoring will be provided to the study site.

- End of Procedure:
 - Collection of BIS™ sensor placement, monitoring of cardiovascular variables, event markers and assessments
- Recovery:
 - Anesthesia Airway management
 - Collection of incidents of post- op nausea
 - Pediatric Anesthesia Emergence Delirium (PAED)

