10.9.3.3 BIS™ Guided Group

In the BIS™ group, sevoflurane will be adjusted to achieve a target BIS™ values of 45 – 60 during maintenance of anesthesia and BIS™ values of 60 – 75 beginning of skin closure. Subjects with BIS™ values that are outside of the specified range of 45 – 60 during maintenance of anesthesia for >35% of the maintenance duration will be considered a protocol deviation and the subject will be excluded from the final data analysis and will be replaced by an additional subject. The excluded subject will continue to be monitored for any safety events and the clinical will ensure that medical care is provided should a safety event occur. Data from the excluded subject will be acknowledged in the final study report but will not be

included in the primary statistical analysis. The exception to this exclusion is any data that is outside of the specified range of 45 – 60 as a result of the anesthesiologist titrating medications as a result of clinical signs or cardiovascular changes defined above. Additionally, data points will be excluded if significant artifact is present or if the sevoflurane concentration or BIS™ value is missing.

At the completion of the surgery, and after confirmation of the return of neuromuscular function, sevoflurane will be discontinued, and discontinuation time will be recorded, and as applicable, extubation will be performed when the patients demonstrate the purposeful movement, facial grimace, or eye-opening to jaw thrust.

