7.4 Handling of Missing, Unused, and Spurious Data and Dropouts

The primary analysis will include all evaluable data and missing values will not be imputed. BIS™ values that are outside of the specified range of 45 – 60 during maintenance of anesthesia for >25% of the maintenance period will be considered a protocol deviation and will result in an exclusion of the subject from the primary analysis. The excluded subject will be replaced, and data from all excluded subjects will be noted and discussed in the final study report. Additionally, sensitivity analysis (e.g., multiple imputation) may be performed as appropriate to assess the robustness of study results.

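### The plan does not say how maintenance minutes without a valid BIS value enter the 35% exclusion rule or the time-in-range summary. Read literally, such minutes loosen the rule and lower time in range, and the BIS arm's time in range may be summarised only in children selected for being in range

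*Protocol*

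**What the plan says.** **Exclusion rule.** Protocol 14.1 (Missing Data) removes a child from the primary analysis, with replacement, when BIS values are "outside of the specified range of 45 – 60 during maintenance of anesthesia for >35% of the maintenance duration". The Synopsis (Study Design; Maintenance anesthesia) and 10.9.3.3 give the same limit under the BIS group. They add an exception for out-of-range data that result from titration for clinical signs or cardiovascular changes. Section 14.1 names no arm and does not repeat the exception. SAP 7.4 has a different limit: "for >25% of the maintenance period will be considered a protocol deviation".

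**Time in range.** Protocol 14.1 (Additional Summaries and Considerations), the Synopsis and SAP 7.9 list "the percentage of time during maintenance with BIS™ value within the specified ranges" for both arms. No formula and no test is given.

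**Minutes without a usable value.** Protocol 10.9.3.3 states: "Additionally, data points will be excluded if significant artifact is present or if the sevoflurane concentration or BIS™ value is missing". The same sentence stands in the BIS-group text of the Synopsis. There is no counterpart for the SP group. Protocol 14.1 adds: "The primary analysis will include all evaluable data and missing values will not be imputed".

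**Who is summarised.** The Synopsis and 10.9.3.3 say that an out-of-range BIS-arm child leaves the final data analysis. They then say that the child's data are left out of the primary statistical analysis. Section 14.1 mentions only the primary analysis.

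**The concern.** Both percentages need a valid BIS value in the numerator, but the rule's denominator is elapsed maintenance time, and time in range reads the same way. The Protocol expects some minutes to have no valid value. Dropping a data point removes it from the numerator; whether it also shortens the maintenance duration is not stated.

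The more important consequence is for the exclusion rule, because it decides which BIS-arm children enter the primary analysis and which are replaced, with only 18 per arm in each age group. If lost minutes stay in the denominator, children with poor signal face a more lenient limit than children with complete recordings.

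For time in range, the stakes are interpretive. The summary describes how well depth was held in each arm. If it covers only children who passed a rule on being in range, and that rule is applied to one arm, part of any difference is built in.

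**Working it through.** **Inputs.** From the documents: the limits of 35% (Protocol) and 25% (SAP 7.4), per-minute recording (Protocol 14.1), 18 per arm per age group (Protocol 14.2), and SP maintenance BIS of 39.6 ± 11.5 in ages 3–18 (Protocol 4.1.3.2, Table 2). The share of maintenance without valid BIS, m, is not given; values below are assumptions.

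**The plan's own figure.** The only computable design figure is power, which is not in dispute. With a difference of 0.5, SD 0.5, 18 per arm and two-sided 0.05, the expected z is (0.5/0.5) × √(18/2) = 3. Power is then 85.1% by the normal approximation and 83.0% by the noncentral t, consistent with the stated figure of more than 80%.

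**Step 1: one child, three readings.** Take 60 minutes of maintenance: 30 in range, 20 out, 10 without valid BIS, none under the titration exception.
- Whole duration, lost minutes in neither numerator (the literal reading): out 20/60 = 33.3%, kept under 35%; in range 30/60 = 50.0%.
- Valid minutes only: out 20/50 = 40.0%, excluded; in range 30/50 = 60.0%.
- Lost minutes counted as out: 30/60 = 50.0%, excluded. The text does not support this, because the rule needs a BIS value outside the range.

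On the literal reading the two shares sum to 50.0 + 33.3 = 83.3%, which is 1 − m with m = 10/60. Under the SAP's 25% limit this child is excluded on every reading.

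**Step 2: effective limit on valid minutes.** Let o be the out-of-range share of valid minutes. The literal rule keeps the child when o(1 − m) ≤ limit, so the largest o that is kept is limit/(1 − m).

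| m (assumed) | 0.35/(1−m) | 0.25/(1−m) |
|---|---|---|
| 0% | 35.0% | 25.0% |
| 5% | 36.8% | 26.3% |
| 10% | 38.9% | 27.8% |
| 20% | 43.75% | 31.25% |
| 30% | 50.0% | 35.7% |

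**Step 3: time in range between arms.** With in-range share p of valid minutes, the literal summary reports p(1 − m). The error in the BIS-minus-SP difference is p(SP) × m(SP) − p(BIS) × m(BIS).
- Equal p and equal m: the error is 0.
- p = 60% in both arms, m = 10% to 20% in SP and 5% in BIS: 0.60 × 0.05 = 3 points to 0.60 × 0.15 = 9 points in favour of BIS.
- Inputs closer to the Protocol: a rough normal reading of 39.6 ± 11.5 puts about 28% of SP values in 45–60 (z from 0.47 to 1.77). Take 65% for BIS, the complement of the 35% limit. At the same missing rates the error is 0.28 × 0.10 − 0.65 × 0.05 = −0.5 points to 0.28 × 0.20 − 0.65 × 0.05 = +2.4 points, against a gap of 65 − 28 = 37 points.
- Those shares with m = 10% in both arms: the gap shrinks to 37 × 0.90 = 33.3 points.

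**Step 4: selection.** With no missing and no exempt minutes, every BIS-arm child who passes the 35% rule is at least 65% in range by construction. SP children have no such floor, since the Synopsis and 10.9.3.3 apply the rule to the BIS group. If the summary uses only retained children, the BIS-arm figure cannot fall below 65% however well or badly titration worked.

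**The case against.** The strongest reply is that the denominator is undefined, not wrong. Data are recorded by minute and unusable points are dropped, so an analyst may compute both percentages on what remains; the asymmetry then vanishes. Section 14 also sends data exclusion to the Data Management Plan, which is not among the documents, and Section 14.2 rejects non-qualifying data sets, which might catch a child with very poor signal. This stands in part: the whole-duration denominator is explicit only for the exclusion rule. But 14.1 promises that analysis details will be in the SAP, and the SAP has none on this. No minimum coverage is given for a qualifying data set.

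A reader might go further and infer that the arm comparison of time in range measures signal loss and flatters BIS. The documents do not support that. They give no missing rates, and they protect the SP signal: "The signal quality index (SQI) number will be visible to the anesthesiologist during the case to capture a good quality signal". The calculation that yields 3 to 9 points needs the same in-range share in both arms, which sits badly with an SP mean BIS of 39.6 in the Protocol's own prior data. With shares nearer those data the error is small and can go either way. Time in range is also an additional summary with no test attached.

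It is also fair that at 5% to 10% missing the effective limit moves only to 36.8% to 38.9%.

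**Conclusion.** The point holds as a gap in definition with a specific consequence. On the literal text, a minute without valid BIS lowers time in range yet cannot count toward exclusion, and the limit on valid minutes rises from 35% to 0.35/(1 − m): modest at 5% to 10% missing, material at 20% or more. These m values are assumptions. How many children would be reclassified cannot be worked out from the documents.

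Time in range is distorted between arms only to the extent that missing shares or in-range shares differ, and neither the size nor the direction is known. A claim of bias toward BIS should not be made. Two further points do not depend on missing rates: the artifact rule is written for one arm only, and the text leaves open whether BIS-arm time in range is summarised only among children retained for being in range. The 35% and 25% limits contradict each other. The SAP says it elaborates version 2.0 of the protocol, before the limit was changed.

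**What to change.** In Protocol 14.1, the matching Synopsis text and 10.9.3.3, and in SAP 7.4 and 7.9:

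1. Define a valid BIS minute by one artifact/SQI criterion that applies to both arms.
2. Compute the out-of-range share and time in range over maintenance minutes with valid BIS.
3. Keep minutes under the clinical-sign titration exception as a separate category. The rule's out-of-range share then need not sum to 100% with time in range, and the plan should say so.
4. Report the share of maintenance with valid BIS by arm, and flag children with low coverage.
5. Summarise time in range for every randomised child with a BIS record, whether or not the child is in the primary analysis.
6. Reconcile the Protocol's 35% with the SAP's 25%.

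No new data are needed: the cost is a definition, wording in the places named, and a coverage row in one table. There are two downsides. Percentages are unstable for children with few valid minutes, which the coverage flag makes visible. The exclusion rule may also reclassify a few children, which affects who is replaced, so the definition should be settled before data are examined by arm.
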